### **7.6 Final Assessment (Visit 4)**

Visit 4, the final visit will occur 74-82 days after Visit 2. Visit 4 will include review and entry of data in the voiding diary, review of current medication list, physical examination including measurement of vital signs, PVR, OAB-q, NMSS, PPBC, and SGI-C. Screening for AEs will also take place during this visit. This will include assessment of symptoms of urinary tract infection and if, in the opinion of the study physician, urinalysis is indicated, dipstick will be performed with reflex to urine culture if positive. In pre-menopausal women, screening for pregnancy risk will be performed and if, in the opinion of the study physician, pregnancy testing is indicated, urine hCG will be measured.

### **7.7 Unscheduled Visits**

Subjects may return to the clinic for safety evaluation or to receive additional study medication as needed. Unscheduled visits will include a review of concomitant medications and any adverse effects, and, if needed in the estimation of the study physician, physical examination in whole or in part.

## **8. STUDY POPULATION**

The population for this study is PD patients with symptoms of OAB who meet all of the following inclusion criteria and who do not meet any of the following exclusion criteria.

### **8.1 Inclusion Criteria**

An eligible patient:

- Has signed and dated an IRB-approved informed consent form before any protocol-specific screening procedures are performed.
- Has a diagnosis of PD consistent with UK PD Society Brain Bank criteria
- Is aged 30 years or older
- Has had no change in PD medications during the 4 weeks preceding screening, with no dose changes during the study, except that PRN (as needed) doses of carbidopa/levodopa will be allowed to address periodic worsening of parkinsonian symptoms.

- Is willing and able to complete micturition diary
- Has urinary urgency as defined by having 8 or more entries of bladder urgency score  $\geq 2$  in a 72-hr voiding diary during screening period
- Has micturition frequency as defined by having 8 or more episodes of micturition per 24 hours, averaged over 72 hours; OR by having at least 2 episodes of incontinence in 72 hours as documented in the voiding diary during screening period
- May use other medications that could influence bladder function, other than those specifically prohibited, as long as the dose is stable for 4 weeks preceding screening, with no dose changes during the study.
- Has valid health insurance coverage at the time of study enrollment and expects this coverage to remain valid for the duration of the study period.

## 8.2 Exclusion Criteria

A patient will be excluded from the study if he or she meets any of the following:

- Is a woman who is breast-feeding, pregnant, or has the potential to become pregnant during the course of the study (fertile and unwilling/unable to use effective contraceptive measures).
- Has cognitive deficits that, in the opinion of the study physician, would interfere with the subject's ability to give informed consent or perform study testing.
- Has at screening a systolic blood pressure  $> 165$  or a diastolic blood pressure  $> 100$
- Has at screening a heart rate  $> 100$
- Has a history of allergy to Mirabegron
- Has at screening a post-void residual  $> 200$ ml
- Has at screening evidence of a urinary tract infection
- Has at screening evidence of chronic inflammation such as interstitial cystitis, bladder stones, previous pelvic radiation therapy, or previous or current malignant disease of the pelvic organs
- Has received intravesical botulinum toxin treatment within six months prior to screening.
- Has the presence of an Interstim device
- Uses an indwelling catheter or self-catheterization
- Concurrent use of thioridazine, flecainide, propafenone, or Digoxin
- Concurrent use of warfarin (Coumadin)
- Use of one of the anti-cholinergic bladder medications specified below within 14 days of the screening visit. Subjects who have used one of these medications in the past but discontinued it at least 14 days prior to the screening visit will not be excluded.
- Has at screening an estimated glomerular filtration rate (eGFR)  $< 60$ , or AST or ALT  $> 2x$  upper limit of normal
- Has any other serious and/or unstable medical condition
- Has participated in other drug studies or has used other investigational drugs within 30 days prior to Screening Visit
- Prohibited anti-cholinergic bladder medications:

Darifenacin (Enablex)  
Fesoteridine (Toviaz)  
Flavoxate (Urispas)  
Oxybutynin (Ditropan, Ditropan XL, Oxytrol, Uromax, Apo-Oxybutynin, Riva-Oxybutynin, Cystrin)  
Solifenacin (Vesicare)  
Tolterodine (Detrol, Detrol LA, Detrusitol, Unidet)  
Trospium (Sanctura, Sanctura XR)

### **8.3 Removal of Patients from Study**

A patient will be considered to have completed the study when he or she has completed all study visits through the final visit. Every patient has the right to discontinue study participation at any time at his/her own request, or may be withdrawn at any time at the discretion of the investigator for safety, behavioral, or administrative reasons. Criteria for early termination include, but are not limited to, < 36 hours of time covered in a bladder diary, poor adherence to study medication (less than 70% of study medication consumed), loss of health insurance coverage, and safety issues related to study-related or non-study related adverse events.

If a patient has a clinical necessity to alter their standard PD medications, the patient will be withdrawn from the trial so that changes may be made, except that occasional additional doses of carbidopa/levodopa will be allowed if needed to address periodic worsening of parkinsonian symptoms. Additional doses of carbidopa/levodopa taken during the 72-hour diary periods will be recorded in the diary. If a patient is withdrawn due to an adverse event, the event will be followed, when possible, until resolution. Patients who withdraw from the study may be replaced, but withdrawn patients will not be re-entered into the study.

All data generated up to the time of discontinuation from the study will be analyzed and the reason(s) for discontinuation will be recorded.

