## **10.2 Efficacy Assessments**

### **10.2.1 OAB-SCS**

The primary outcome measure will be the change in the mean daily Overactive Bladder-Symptom Composite Score (OAB-SCS) from baseline to visit 4. . One of the secondary outcome measures will be the change in the mean daily OAB-SCS from baseline to visit 3. The OAB-SCS requires subjects to record the severity of urgency of each micturition over a 72-hour period as follows: 1 = no urgency (normal voiding); 2 = mild (could postpone voiding for as long as necessary without fear of incontinence); 3 = moderate (could postpone voiding for a short while without fear of leakage); 4= severe (could not postpone, had to rush to the toilet); 5= urgency incontinence (could not make it to the toilet without some leakage). The total score is derived by adding the urgency rating of each micturition over a 72-hour period as recorded in a voiding diary. In this way, the OAB-SCS accounts for both frequency and urgency in OAB, and is therefore a more accurate assessment of OAB than measurements of urgency alone (Starkman 2008). Mean daily OAB-SCS is total 72-hour score divided by 3. For incomplete days, the daily score will be adjusted to equal [(total score for the incomplete day / actual number of hours recorded) x 24 hours] (Zinner 2005).

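### A short Visit 3 diary can end participation under Section 8.3 and so cost a randomised subject the Visit 4 primary outcome

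*Protocol*

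**What the plan says.** Section 8.3 of the protocol states that a patient "may be withdrawn at any time at the discretion of the investigator for safety, behavioral, or administrative reasons". The next sentence gives the grounds for early termination, and the first of them is "< 36 hours of time covered in a bladder diary". No diary is named, so the wording covers the screening diary and both later ones. The section continues: "Patients who withdraw from the study may be replaced, but withdrawn patients will not be re-entered into the study". It also says "All data generated up to the time of discontinuation from the study will be analyzed", but schedules no visit or diary after withdrawal.

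Section 10.2.1 fixes what each diary is for. On Visit 4: "The primary outcome measure will be the change in the mean daily Overactive Bladder-Symptom Composite Score (OAB-SCS) from baseline to visit 4". On Visit 3: "One of the secondary outcome measures will be the change in the mean daily OAB-SCS from baseline to visit 3". Sections 7.4.3 and 7.5.2 show that these are the only two diaries after randomisation. Section 11.2 defines the study population as all patients who pass screening and are randomised, analysed by intent to treat.

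**The concern.** The criterion treats a data-quality problem at one visit as a reason to stop observing the subject. Before randomisation that does no harm: a person who cannot keep the screening diary need not enter the trial. After randomisation the effect differs. An incomplete diary at Visit 3 weakens a secondary measurement, but withdrawal on that ground also forfeits the primary measurement, which the subject might well have provided.

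Two things are at stake. The first is missing primary outcomes that the trial creates itself, in a study of 20 per arm. The second is the meaning of the intent-to-treat analysis. If the investigator decides after randomisation who goes on to give a primary outcome, the subjects with Visit 4 data are a selected set, even when that decision is blinded. A statistical analysis plan can say how missing Visit 4 values are handled. It cannot recover a diary that was never kept.

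**Working it through.** The protocol states no figure on this point that could be reproduced, so the check is of timing, then of consequence, then of scale.

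**Timing** (Sections 7.5.1, 7.5.2 and 7.6, days counted from Visit 2)
- Visit 3: day 32 to 40. Visit 4: day 74 to 82.
- Shortest gap: 74 − 40 = 34 days. Longest gap: 82 − 32 = 50 days.
- The prompt for the Visit 4 diary comes at Phone Visit 2, day 70 to 74, which is 70 − 40 = 30 to 74 − 32 = 42 days after Visit 3. Withdrawal at Visit 3 therefore always precedes the primary diary.

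**Consequence, reading the sections together**
1. Section 8.3 permits termination for a short diary and does not exempt the Visit 3 diary.
2. Section 8.3 bars re-entry and provides no later assessment.
3. Section 10.2.1 needs the Visit 4 diary for the primary outcome, so that outcome is missing.
4. Section 11.2 still counts the subject in the analysis. A replacement under Section 8.3 restores the head count but not the outcome of the person originally randomised.

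Section 10.1.5 provides a useful contrast. A subject who stops study drug early because of urinary retention symptoms may still complete other study elements. Section 10.1.2 says the same for the vital-sign limits, although Section 7.4.1 speaks of withdrawal there; those two need reconciling, but that is a separate matter. The protocol thus already separates stopping drug from stopping observation, and does not do so for a short diary.

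**Scale** (assumed rates, since the protocol gives none)
- Subjects affected, if every short Visit 3 diary led to withdrawal: 0.05 × 40 = 2; 0.15 × 40 = 6.
- Difference detectable with 80% power, two-sided 0.05, in SD units: (1.960 + 0.842) × √(2/n), with n per arm.
- Power at a true difference of 0.886 SD: Φ(0.886/√(2/n) − 1.960).

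| Loss (assumed, equal in both arms, no replacement) | n per arm | Detectable difference | Power at 0.886 SD |
|---|---|---|---|
| 0% | 20 | 0.886 SD | 80% |
| 5% | 19 | 0.909 SD | 78% |
| 10% | 18 | 0.934 SD | 76% |
| 15% | 17 | 0.961 SD | 73% |

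The table is for orientation only. Section 11.1 does not derive the 40 subjects from a power calculation.

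**The case against.** The strongest reply is that the rule is discretionary. The investigator may keep a subject with a short Visit 3 diary, so no loss is automatic. That stands: the text permits the loss and does not require it, and the 2 to 6 subjects are an upper reading of the assumed rates.

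The protocol also has safeguards that should keep short diaries uncommon: training at screening (7.3), willingness and ability to keep the diary as an inclusion criterion (8.1), exclusion of cognitive deficits that would interfere with testing (8.2), review of a screening diary before randomisation (7.4.1), and a telephone prompt before each later diary (7.4.3, 7.5.2). These stand too. Nothing in the protocol shows that short diaries would cluster in sicker subjects or differ between the blinded arms. At the low end the loss of precision is small, and this is an exploratory pilot.

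A reader might go further and infer that a Visit 4 diary under 36 hours is bound to be scored, because Section 10.2.1 ("For incomplete days, the daily score will be adjusted to equal" a 24-hour value) sets no minimum coverage and Section 8.3 analyses all data up to discontinuation. The protocol does not say so for Visit 4, and a minimum for scoring is commonly left to the statistical analysis plan, which is not at hand. Nor does it follow that short Visit 4 diaries should be voided. That would turn observed primary values into missing ones. A 36-hour total would also not screen out partial-day recording, since three days of 12 hours reach exactly 36.

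What the reply does not answer is why an incomplete secondary diary should ever be a ground for giving up the primary one.

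**Conclusion.** The point holds for the Visit 3 diary. As written, Section 8.3 allows a randomised subject to be withdrawn for a short secondary diary, 34 to 50 days before Visit 4, with the primary outcome lost for good. This works against the intent-to-treat analysis in Section 11.2, and no analysis plan can repair it afterwards.

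The size is unknown. The range of 2 to 6 subjects rests on an assumed 5% to 15% of short Visit 3 diaries and on withdrawal in every such case. Without replacement and with equal loss in both arms, the detectable difference would rise from 0.886 SD to between 0.909 and 0.961 SD. No direction of bias between arms can be claimed. The point is a minor suggestion, worth making because the change costs almost nothing.

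**What to change.** In Section 8.3, take diary coverage under 36 hours off the list of grounds for early termination after randomisation. Add one sentence: a subject whose Visit 3 diary falls short stays in the study and keeps the Visit 4 diary. For the screening diary, keep the threshold as a ground for not randomising, and cross-refer to Section 7.4.1, where that diary is reviewed.

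The change is to wording only. It leaves the other termination criteria and the scoring in Section 10.2.1 as they are. The cost is that a few subjects with poor diary compliance remain in follow-up, and some of them may return an incomplete Visit 4 diary as well.

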### **8.4 Screen failures / Rescreening**

Subjects who screen fail because they do not meet inclusion criteria or because of certain exclusions, e.g. presence of urinary tract infection, may rescreen after 30 days at the discretion of the investigator.

## **9. TREATMENTS**

### **9.1 Behavioral Modification with Pelvic Floor Exercise (BM-PFE) Educational Material**

We will produce a 15-20 minute presentation, written by a physical therapist, utilizing a PowerPoint presentation. Slides will include images such as pelvic floor anatomy as well as outlines of key points. Participants will be given a paper copy of the presentation to take

home for reference and to help them with a home bladder exercise regimen. The following topics are part of this presentation:

- Bladder health: What's normal?
- Bladder dietary irritants
- Bladder retraining and urge delay techniques
- Pelvic floor anatomy and function
- How to perform a "Kegel"
- "Kegel" home exercise program
- Pelvic floor exercises with functional activities
- Maintaining your home exercise program

Subjects will have the opportunity to ask the study physician follow-up questions as needed.

## **9.2 Investigational drug**

The study medication and matching placebo will be provided by Astellas. The active medication will be mirabegron 25 mg po daily from Baseline Visit (Visit 2) to Titration Visit (Visit 3). At the Titration Visit, all patients who have tolerated mirabegron 25 mg daily (no adverse events on this dose) will be up-titrated to mirabegron 50 mg daily. This will be dispensed as two 25-mg tablets or, for those in the placebo arm, two placebo tablets. Only those without any AE on 25 mg daily or matching placebo will be eligible to increase the dose. The research pharmacist will dispense the active or placebo medication at randomization and again at the Titration Visit. An extra 5-day supply of medication will be provided for each study period to allow a window for scheduling of appointments.

## **9.3 Randomization and Blinding**

Following confirmation of eligibility at Visit 2, an eligible patient will be randomized in a 1:1 randomization scheme to receive mirabegron 25 mg daily or placebo. Randomization will occur at the research pharmacy of EvergreenHealth using a computer-generated randomization list. The pharmacist will maintain a codebook indicating the treatment allocation of each subject. Study medication will be delivered by the research pharmacist to the research study staff from the research pharmacy (a separate locked room containing only research medications). The investigating physicians, nurse and research coordinator will be blinded as to treatment arm until the code is broken. The randomization code may be broken by the investigator only in a medical emergency. The reasons for this will be documented carefully. The subjects will receive identical appearing active or placebo study medication tablets, with identification known only to the research pharmacist.

## **9.4 Concomitant Therapy**

All concomitant therapy will be documented. Prohibited will be concurrent (defined as "within 14 days of screening") use of antimuscarinics listed in Appendix 3: oxybutynin (Ditropan®, Ditropan XL ®, Oxytrol ®, Uromax ®, apo-oxybutynin, riva-oxybutynin,

Cystrin®), tolterodine (Detrol®, Detrol LA®, Detrusitol®, Unidet®), fesoterodine extended-release (Toviaz®), solifenacin (Vesicare®), trospium (Sanctura®, Sanctura XR®), flavoxate (Urispas®), and darifenacin extended release (Enablex®). Also prohibited will be concurrent use of thioridazine, flecainide, propafenone or Digoxin; and intravesical botulinum toxin treatment within the previous six months. Medications that are likely to influence bladder function may not be initiated between screening and study completion. They may be continued with no dose changes during the study.

## **9.5 Treatment Compliance**

Patients will be asked to return all unused medication and all medication bottles, including empty bottles, at each visit and at the end of the study and the quantity of returned medication will be documented.

# **10. DESCRIPTION OF ASSESSMENTS**

## **10.1 Safety Monitoring**

Safety will be monitored by adverse event (AE) reporting, physical examination, vital signs, laboratory evaluation, and evaluation of post-void residual.

### **10.1.1 Physical Examination**

A general physical examination will be performed at Visit 1 (Screening Visit) and Visit 4 (Final Visit). This exam will include, at minimum, HEENT, heart, lungs, abdomen, musculoskeletal, and neurologic systems. Subjects with a range of health conditions that may put the patient at risk for adverse outcomes will be excluded, as listed under Exclusion Criteria.

### **10.1.2 Vital Signs**

Vital signs (blood pressure, heart rate, and respiratory rate) will be measured at each clinic visit. Subjects with BP > 165 systolic or > 100 diastolic or those with HR > 100 will be excluded at screening or discontinue study medication if this occurs while on study medication. However, they may complete other elements of the study.

### **10.1.3 Laboratory Evaluations**

All subjects will undergo baseline testing with CBC, CMP, and urinalysis by dipstick with reflex to urine culture if positive. Subjects with screening estimated glomerular filtration rate (eGFR) < 60, or AST or ALT > 2x upper limit of normal will be excluded.

### **10.1.4 Pregnancy Status**

All pre-menopausal women will have pregnancy screening with urine hCG at baseline (Visit 1). At Visits 3 and 4, pre-menopausal women will have screening for pregnancy risk and if, in the opinion of the study physician, pregnancy testing is indicated, urine hCG will be measured. A positive urine hCG will result in discontinuation of the study drug and withdrawal of the subject from the study.

#### 10.1.5 Post-void Residual

PVR will be measured by a bladder scan after urination at Visits 1, 3, and 4. Subjects with PVR > 200 mL will be excluded at screening or will discontinue study medication if this occurs while on study medication. Symptoms of urinary retention will be monitored throughout the study and may lead to early discontinuation of study medication; however, such subjects may complete other elements of the study.

#### 10.1.6 Adverse Events

*Subjects will be monitored for adverse events throughout the trial. The occurrence of adverse events will be ascertained by observation, telephone monitoring and questioning by the investigator. Safety assessments will consist of monitoring and recording all adverse events, including serious adverse events.*

An adverse event (AE) is any symptom, physical sign, or medical condition that emerges during the study or, if present at screening, worsens during the study, regardless of the suspected cause. Adverse events include adverse drug reactions, illness with onset during the study, exacerbations of pre-existing conditions or clinically significant changes in physical examination or significantly abnormal objective test findings. Medical conditions/diseases present before starting study treatment are only considered adverse events if they worsen after starting study treatment. All adverse events will be recorded and graded as mild, moderate or severe by the principal investigator in accordance with general guidelines of clinical research, outlined here:

- **MILD:** An event that causes transient or minimal symptoms and that does not interfere with daily activities.
- **MODERATE:** An event that causes symptoms sufficient to interfere with but not prevent daily activities.
- **SEVERE:** An event that prevents normal, everyday activities.

Adverse events will also be classified by their relationship to the study medication by the principal investigator in accordance with general guidelines of clinical research, outlined here:

- **Definitely Unrelated:** The AE is definitely not related to the drug. This designation is reserved for those events that do not follow a reasonable temporal sequence following drug administration (e.g. occur prior to study treatment) or for those events that cannot be even remotely related to study participation.

- **Unlikely related:** There is no reasonable association between the study treatment and the suspected event and the event could have been produced by the patient's clinical state or other therapy administered to the patient.
- **Possibly related:** The suspected AE may or may not follow a reasonable temporal sequence from study treatment administration but seems to be the type of reaction that cannot be dismissed as unlikely. The event could have been produced or mimicked by the patient's clinical state or other therapy administered to the patient.
- **Probably related:** The suspected AE follows a reasonable temporal sequence from study treatment administration, abates upon discontinuation of the treatment, and cannot be reasonably explained by the known characteristics of the patient's clinical state or other treatments.
- **Definitely related:** The suspected AE follows a reasonable temporal sequence from study treatment administration, abates upon discontinuation of the treatment, and, if appropriate, resumes upon re-introduction of the treatment. Additionally, the suspected AE cannot be reasonably explained by the known characteristics of the patient's clinical state or other treatments.

The principal investigator and all other research staff except the research pharmacist will be blinded towards randomization of active drug versus placebo until after completion of study.

